### 6.8 Definition of end of study

The end of study date will be the Last Subject Last Visit (LSLV) date. The trial will end when all randomized subjects who have received the IMP at least once, have completed/discontinued from the study as per trial protocol.

A clinical trial protocol may not be considered closed as long as:

- Any subject is still receiving any investigation medicinal product (IMP).
- Visits specified by the protocol are still taking place.
- Procedures or interventions according to the protocol are still being undertaken in any subject.
- The post-treatment follow-up period, defined in the clinical trial protocol as being part of the trial, has not yet been completed for any subject.

Any clinically relevant deviations from baseline findings for all subjects observed at end of trial examination have to be monitored until they have either returned to normal, are no longer considered clinically relevant, or can be explained.

In case of pregnancy All efforts should be made for postpartum follow-up and child development up to 1 year of age so that we can assess their psychomotor development. Any SAE experience during pregnancy must be recorded in the SAE Notification Form.

7 PPD / Site and form of  
confinement of the research participants

PPD

7.2 Form of confinement of the research participants

The healthy research participants will remain confined in the premises of Clinical Unit of PPD PPD, under the responsibility of the medical team and under the care of the nursing team. For this study, will be selected 72 participants who will be admitted into two equally subgroups (36 participants in each subgroup divided equally between gender and sequences). The participants will be received at around 7 p.m. on the day previous to the beginning of collections. On the day of drug administration, the nursing professional will start the routine procedures predicted for the participant during confinement including measurement of systolic blood pressure, diastolic blood pressure, heart rate, and temperature. The pharmacist in charge will release the medication following the list of randomization contained in the protocol (Annex 6), also providing to the nursing professional and the team involved in the collection of blood samples, the instructions related to the protocol. Therefore, the phlebotomists will install the heparinized intravenous catheters to perform the collections of sample zero (pre-dose) and those predicted throughout the day. The staff in charge for the collection will remain at the confinement site throughout hospitalization. There will be frequent visits of the nursing team to the bed where each participant is kept during the entire hospitalization period.

8 PPD / Treatments of study

8.1 PPD / Test and comparator drugs

Tabela 1 – Medicamentos teste e comparador utilizados no estudo / Test and comparator drugs

Amostras Formulação Teste* / Test Formulation samples*	
PPD / Medication	Eutirox®
PPD / Manufacturer	Merck, S.A. de C.V.
PPD Address	Darmstadt, Germany.
PPD / Active ingredient	PPD / Levothyroxine sodium
PPD / Pharmaceutical form	PPD / Tablet
PPD Concentration	PPD
PPD / Observations	PPD Store at room temperature (15°C to 25°C). Protect from light and humidity.
PPD / Comparator Formulation samples*	
PPD / Medication	
PPD Manufacturer	Sanofi-Aventis Farmacêutica Ltda.
PPD / Address	[name]
PPD / Active ingredient	PPD / Levothyroxine sodium
PPD / Pharmaceutical form	PPD / Tablet
PPD Concentration	
PPD / Observations	PPD Store at room temperature (15°C to ty.

PPD

PPD e same batches of Test and Reference Drugs used in the Pharmaceutical Equivalence study must be mandatorily used.

PPD

As predicted on Resolution – RE # 1170 dated 4/19/2006, the hospitalization can only be started after the issue of the conclusive report of pharmaceutical equivalence between test and reference formulations, and the content difference between the products is not higher than 5%.

PPD

should be recorded on forms as Annexes 1 and 2, respectively, and they should be entered into the clinical report.

PPD

## 8.2 Dosage

At every period, the research participant will receive orally a dose of 600mcg of Levothyroxine sodium corresponding to 03 tablets of test drug **or** 03 tablets of comparator drug according to the randomization list (Annex 6), together with 200mL of water after a fasting period of 8 hours. The participants will be instructed that the drugs under tablet form should be eaten whole, cannot break them or chew the drug and the oral suspension completely swallowed. After the administration of the drug the research participants must remain seated (approximately 90° position) during the 01 hour.

PPD

### 8.2.1 Justification for dose

[figure not shown]
According to the local legislation RE1170, in general it is sufficient to carry out single-dose studies to determine Bioequivalence. Where it is not feasible to differentiate from basal concentrations after administration of a conventional dose, the administration of an increased single dose may be accepted in exceptional cases to allow appropriate quantification of the drug, provided that this dose does not exceed the maximum tolerated dose per day, which must be previously justified in the clinical protocol.

The FDA Guide - Guidance for Industry Levothyroxine Sodium Tablets — In Vivo Pharmacokinetic and Bioavailability Studies and In Vitro Dissolution Testing, describes that a high dose of levothyroxine should be administered (600ug) to detect T4 above at baseline levels.

For this study, will be administer a dose of 600 µg (3 tablets of the 200 µg strength) for comparator and test product to ensure adequate pharmacokinetic determination, and accuracy measurement of the analyte.

9

PPD

**9.1 Fasting and feeding times**

*The night before drug administration the research participants will go to the Clinical Unit of PPD and must have their last meal until 11.00 p.m., and they will remain in fast un sing, which is estimated for the following morning.*

*In order to maintain the standardization of the treatment groups, the diet (food and liquids) to be provided will follow the same standard, in two periods of confinement, for all research participants and must be free of fried and fat foods. To plan the menu, the nutrition professional will use as caloric reference the established in Ordinance # 193 dated 12/5/2006, article 5, paragraph 3 of the Worker Feeding Program ("PAT"). This way the meals provided will follow the following caloric quantities:*

- *Main meals (lunch and dinner): must contain from 684 to 930 calories;*
- *Minor meals (snack): must contain from 300 to 400 calories;*
- *Minor meals (breakfast in extra collections and snack into 36 hours collection): must contain from 170 to 200 calories.*

*The person in charge for the clinical step will provide the instructions to the Nutrition Service about the standardized diet that will be provided to the healthy participants, also highlighting the prohibition of the intake of beverages or foods containing caffeine or xanthines (black and mate tea, coffee, cocoa milk, cola sodas, guaraná, foods containing chocolate and others). The composition of the meals is on Annex 7.*

**Meal times:**

- *Dinner - minimum of 8 hours of fasting;*
- *Lunch – 4 hours after the administration of the drug;*
- *Afternoon snack - 8 hours after the administration of the drug;*
- *Dinner - 12 hours after the administration of the drug.*

**Liquids:**

- *Water is allowed – until 7 hours before the administration of the drug and after two hours of the administration of the drug;*
- *Immediately after the administration of the drug – 200 mL of water;*
- *Prohibited ingestion of liquids – from 7 hours before the administration of the drug until two hours after the administration of the drug, except 200mL of water that will be given at the time of drug administration.*

PPD

PPD A scheme of the activities performed by the research participant in study periods 1, 2 and 3 is described on Table 2 below:

PPD / Table 2 -  
 Activities performed by the research participant in study periods 1 and 2.

PPD			
POOL	PPD Before tration	15mL	
C-1	-00:30 (PPD / baseline	7,5mL	
C-2	-00:15 (PPD / baseline	7,5mL	
C-3	00:00**	7,5mL	PPD / BP, pulse, temperature
C-4	00:30	7,5mL	PPD
C-5	01:00	7,5mL	PPD / BP, pulse, temperature
C-6	01:30	7,5mL	PPD
C-7	02:00	7,5mL	PPD / BP, pulse, temperature
C-8	02:30	7,5mL	PPD
C-9	03:00	7,5mL	PPD / BP, pulse, temperature
C-10	03:15	7,5mL	
C-11	03:30	7,5mL	
C-12	03:45	7,5mL	PPD
C-13	04:00	7,5mL	PPD / BP, pulse, temperature
C-14	04:15	7,5mL	
C-15	04:30	7,5mL	
C-16	04:45	7,5mL	PPD
C-17	05:00	7,5mL	PPD / BP, pulse, temperature
C-18	05:30	7,5mL	PPD
C-19	06:00	7,5mL	PPD / BP, pulse, temperature
C-20	06:30	7,5mL	
C-21	08:00	7,5mL	PPD / BP, pulse, temperature
C-22	10:00	7,5mL	
C-23	12:00	7,5mL	PPD / BP, pulse, temperature

PPD				
C-24	24:00	7,5mL	PPD	/ BP, pulse, temperature*
C-25	36:00	7,5mL		/ BP, pulse, temperature*
C-26	48:00	7,5mL		/ BP, pulse, temperature*
C-27	72:00	7,5mL		/ BP, pulse, temperature*
PPD / *If necessary.				
PPD / **5 minutes before drug administration.				

**9.2 Chronogram of sample collection**

The collections will be performed through heparinized intravenous catheter inserted into a superficial vein of the research participant using 7,5mL tubes containing the anticoagulant EDTA and labeled with the number of participant, number of data collection, study period, the active code (LVT) and number protocol. After each blood collection, the catheter is washed with 1mL of sodium heparin. Before each collection the heparin solution inserted to wash the intravenous catheter will be removed. Before the administration of the study drug (Period 1 and 2) a blood collection of 15mL (pool) that will be required for the validation of the analytical methodologies and will be used to constitute the plasma bank of all research participants for the preparation of the standard curves to be used during the study. In total will be collected 54 blood samples of 7,5mL and 2 blood samples each (pool) of 15mL, as established on Table 2. The total volume of blood including 15mL from screening and post-study will be of no more than 465mL of blood per participant. Will be measured blood pressure, pulse and temperature of the research participant in the clinical evaluation pre-confinement and clinical evaluation of discharge from confinement. During in period of the confinement vital signs will be checked at pre-established times to Table 2. When the set time for measurement of vital signs coincide with the time of collection should be prioritized to collect blood, and accepted a range of ±30 minutes for the measurement of vital signs. Vital signs measured during the confinement period will be described in the report of the clinical study. It is important to highlight that the research participant will be released hospitalization after of the 12 hours collection and they will return for the 24:00, 36:00, 48:00 and 72:00 hours. For the extra collections an interval of ± 1 hour of the actual time of collection described in the clinical protocol will be accepted. The extra collections held outside the range if ± 1 hour of provided time will be considered in clinical report as a deviation of protocol. For the collections held during the period of confinement, all delays and advanced shall be considered as deviation of protocol. The actual times of collection will be described in the Clinical Report.

**9.3 PPD**  
**PPD Procedures for the handling and storage of biological samples**

PPD

**9.3.1 Internal transportation of biological samples**

A professional from the samples processing lab will collect the tubes containing the blood sample of each one of the research participant, immediately after the collections. These samples will be placed in appropriate racks, inside a thermal box, containing solid ice and with temperature control (2 – 8°C). The internal transportation of biological samples will be performed through ramps, whereas the research participant flow, clothes, food, and drugs distribution times must not coincide with the internal transportation of the biological samples.

PPD

**9.3.2 Identification of the samples**

*All the sample storage tubes must be labeled with the following information:*

- *Research participant number (01);*
- *Collection number (C-02);*
- *Period of treatment (1 or 2);*
- *In cases of retain samples: (R);*
- *Active ingredient code (LVT);*
- *Biological matrix (plasma)*
- *Number of protocol.*

PPD

### 9.3.3 Handling and storage

Right after the collection, all the test tubes from the same time must be submitted to the Laboratory of Preparation of Biological Samples at the PPD clinical site, where they will be separated in racks and centrifuged at 3000rpm for 5 minutes, at about 4°C.

After centrifugation, using appropriate pipettes, plasma must be separated from sediment and distributed into storage tubes. Two storage tubes (tube containing the samples for analysis + tube containing retention samples) with approximate 2mL of plasma each will be frozen and stored in a freezer (-20°C) with temperature control. The maximum time between blood collection and the centrifugation of samples should not exceed 60 minutes and the time between the centrifugation and the storage of samples should not exceed 60 minutes, except the pool and the collection pre-dose (collection 1).

After frozen, the samples will be organized by study period and stored in plastic bags labeled with the protocol number, active's principle code, number of research participants and study periods (Period 1 or 2) and in the case of samples retains the description "R". Only if the samples destined to the analysis are submitted to the analytical unit of PPD. The retention Biological samples will be stored in accordance with Resolution N° 441 of 12 May 2011 the National Health Council under the responsibility of PPD and will be discarded after the authorization of the sponsor.

PPD

### 9.3.4 External transportation and submission of the biological samples from clinical step to analytical step

Samples should be placed in a properly identified Styrofoam box containing enough dry ice to maintain the freezing temperature of the samples. During transport the internal temperature of the Styrofoam box will be monitored by a calibrated thermometer.

The samples will be transported by own car and by a properly trained technician.

The samples for analysis will be transported followed by Delivery Check List and Biological Samples Checking (RQ-027) listing the box content, the number of samples and other information related to the study. The retention sample will stored at the center and can be shipped later when requested.

The person responsible for the analytical step must receive and check the samples immediately after receiving them, writing down the temperature at the moment of receipt and signing the Delivery Check List and Biological Samples Checking.

## 10PPD / Adverse reactions and

### 10.1PPD / Adverse events (AE)

PPD

#### 10.1.1 Definitions

An **Adverse Event (AE)** is an untoward medical occurrence harmful to health occurring in a clinical investigation participant who has received the drugs related to the investigation and has not necessarily a causal relation to the procedure and/or study drug.

An AE may, therefore, be an unfavorable and non-intentional sign (including abnormal lab findings or vital signs), or a disease temporarily associated or not to the drug.

It is important to explain to avoid confusion, that the adverse events are classified according to their nature and intensity. Therefore, there are differences between **Severe Adverse Event** and **Serious Adverse Event**. The definition of ICH topic E2A (Guide for Clinical Safety Data Management: Definitions and Standards for Expedited Reports) follows below for the differentiation of the terms “severe” and “serious”:

The term “severe” is frequently used to describe the intensity (severity) of a specific event (such as mild, moderate, or severe myocardial infarction); however, the event itself may be of relatively lower clinical importance (such as severe headaches). This definition is not the same for “serious”, which is based on the event outcome for the patient/participant usually associated to events representing a life threat to the patient or him/her inability (as described above).

“Seriousness of the event” is not a synonym of “severity of the event”.

This way we have:

- Classification of Adverse reaction regarding its nature (serious and non-serious);
- Classification of the Adverse reaction regarding its intensity (mild, moderate, severe and lethal);
- Classification of the Adverse reaction regarding the study drug (suspected and non-suspected);
- Classification of Adverse reaction regarding frequency (once, continuous and intermittent)
- Classification of Adverse reaction regarding clinical outcomes: recovered, not recovered, in recovery, recovered with sequel, worsening and death.

PPD

**10.1.2 Classification of Adverse reaction regarding its nature**

A **Serious Adverse Event (SAE)** is any untoward medical occurrence resulting in:

- Death;
- Life-threatening (the term life threatening refers to a reaction where the patient or participant is at risk of death at the moment the reaction occurs, it does not refer to a reaction that could have caused death, if it had occurred with a higher intensity);
- Persistent or significant disability/incapacity;
- Congenital abnormality/birth defect;
- Clinically important effect, including effects by use not indicated in the package insert or abuse (the term clinically important effect must be considered when a reaction is dangerous or requires intervention to prevent the other outcomes described in this definition);
- Requires patient hospitalization or prolongation of an already existing hospitalization (Hospitalization is defined as admission to a hospital site, even if for a period of less than 24 hours). The following hospitalizations are excluded:
  - Treatment of a preexisting condition that is listed in the clinical history and has been planned before the study;
  - Due to social problems;
  - Established in the protocol as part of the study procedures;
  - Emergency treatment of a participant for an event that does not meet the SAE definitions provided above and do not result in hospitalization;
  - Elective (plastic surgery).
- Clinically important effect: the medical and scientific evaluation must be exerted in order to decide if other situations must be considered serious as the clinically important effects not leading to the patient's immediate death or life-treat or hospitalization, but that require intervention to prevent one of the other outcomes listed above. Examples of such events are intensive care in a room or emergency room for allergic bronchospasm, blood dyscrasias, or seizure that does not result in hospitalization or development of drug dependence or drug abuse (ICH-E2A).

Information about common adverse effects already known about the investigational product is described in the product pharmacology (item 1.3.5) and in the Informed Consent Form.

PPD

**10.1.3. Classification of the adverse reaction regarding intensity**

- *Mild*: adverse event of little importance and short duration; may require treatment but does not substantially affect the normal life of the research participant;
- *Moderate*: an adverse event that alters the normal activity of the research participant, resulting in transient disability without sequelae, causes hospitalization, prolongation of hospitalization, attention in emergency service or absence from work;
- *Severe*: an adverse event that directly threatens the life of the research participant, causes congenital anomalies, results in permanent or significant disability, or requires intervention to prevent sequelae;
- *Lethal*: an adverse event leading to death.

PPD

PPD / Table 3 – Relation between adverse events and study drug.

PPD / Suspected	PPD  Temporal relation of the clinical event to the administration of the investigational products makes a causal relationship possible, and other drugs, therapeutic interventions, or essential conditions does not provide sufficient explanations for the event seen.
PPD / Unsuspected	PPD  Temporal relation of the clinical event to the administration of the investigational product makes the causal relationship unlikely, and other drugs, therapeutic interventions, or essential conditions provide sufficient explanations for the event seen

PPD / Table 4 - Classification of adverse event

PPD / Once	PPD / Adverse event occurred only once
PPD / Continuous	PPD  resolution between courses or treatment cycles.
PPD / Intermittent	PPD  The adverse event occurs and resolves during a cycle, course of treatment and then occurs again in another cycle, course of treatment.

PPD

PPD

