### /Drug interactions

PPD

Drug interactions with levothyroxine are:

**Antiarrhythmics:** Amiodarone can inhibit the conversion (iodination) of thyroxine to triiodothyroxine, which results in a decrease in triiodothyroxine concentration and a consequent increase in reverse triiodothyroxine (MARTINDALE, 2002).

**Antibacterials:** rifampicin-induced enzymes increase the metabolism of thyroid hormones resulting in a reduced concentration of them (MARTINDALE, 2002).

**Anticoagulants:** Thyroid hormones increase the effects of oral anticoagulants (MARTINDALE, 2002).

**Antidepressants:** Some drugs, such as lithium, act directly on the thyroid and inhibit the release of thyroid hormones (MARTINDALE, 2002).

**Antidiabetics:** The use of medication can affect the state of the disease and its treatment. In hypothyroid diabetics, the use of levothyroxine may increase the need for insulin or oral hypoglycemic agents (MARTINDALE, 2002).

*Antiretrovirals: Combination of levothyroxine with antiviral, such as ritonavir, may lead to increased use of levothyroxine (MARTINDALE, 2002).*

*Antiepileptics: Some drugs such as carbamazepine, phenytoin or barbiturates may increase the metabolism of thyroid hormones (MARTINDALE, 2002).*

*Gastrointestinal drugs: Sucralfate reduces the absorption of levothyroxine by the gastrointestinal tract, as well as aluminum hydroxide and calcium carbonate (MARTINDALE, 2002).*

*Estrogenic derivatives: estrogenic derivatives may decrease the therapeutic effect of thyroid products (MARTINDALE, 2002).*

*Acetylsalicylic acid can alter thyroid function parameters by competing with thyroid hormones in binding to the carrier proteins (TBG mainly) (MARTINDALE, 2002).*

**1.3.5** PPD /

PPD

PPD

*Very common reaction ( $\geq 1/10$ )*

*Common reaction ( $\geq 1/100$  and  $< 1/10$ )*

*Unusual reaction ( $\geq 1/1.000$  and  $< 1/100$ )*

*Rare reaction ( $\geq 1/10.000$  and  $< 1/1.000$ )*

*Very rare reaction ( $< 1/10.000$ )*

*Unknown reaction (cannot be estimated from the available data)*

*In general, the adverse reactions of levothyroxine are associated with an excessive dosage and correspond to the symptoms of hyperthyroidism.*

- *Heart disorders*

*Very common: palpitations.*

*Common: tachycardia.*

*Unknown: cardiac arrhythmias and angina pain.*

- *Skin and subcutaneous disorders*

*Unknown: rash, hives and sweating.*

- *Psychiatric disorders*

*Very common: insomnia.*

*Common: nervousness.*

*Unknown: excitability.*

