- *Musculoskeletal and connective tissue disorders*

*Unknown: muscle weakness and cramps, osteoporosis in suppressive doses of levothyroxine, especially in postmenopausal women, especially when treated for a long period.*

- *Vascular disorders*

*Unknown: hot flashes, circulatory collapse in preterm low birth weight infants.*

- *Disorders of the reproductive system and breast*

*Unknown: menstrual irregularities.*

- *Gastrointestinal disorders*

*Unknown: diarrhea and vomiting.*

- *Investigations*

*Unknown: weight loss.*

- *Nervous system disorders*

*Very common: headache.*

*Unknown: tremors, benign intracranial hypertension particularly in children.*

- *General disorders and administration site conditions*

*Unknown: heat intolerance, fever.*

- *Endocrine disorders*

*Common: hyperthyroidism.*

*Such effects generally disappear with reduced dosage or temporary withdrawal of treatment.*

PPD

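### The grade Severe in 10.1.3 is defined by consequences, mostly seriousness criteria, although 10.1.1 says that severity means intensity

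*Combined protocol and SAP*

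**What the plan says.** **Terms.** Section 10.1.1 explains that severe "is frequently used to describe the intensity (severity) of a specific event", and that "the event itself may be of relatively lower clinical importance (such as severe headaches". It contrasts this with serious, which rests on the outcome of the event, and states that the two are not synonyms.

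**Seriousness.** Section 10.1.2 lists the SAE criteria. They include death, threat to life, congenital abnormality, "Persistent or significant disability/incapacity", hospitalization or its prolongation, and a clinically important effect, meaning one that is dangerous or "requires intervention to prevent the other outcomes described in this definition".

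**Intensity.** Section 10.1.3 has four grades. Mild and Moderate refer to effect on normal life or activity. Moderate also takes in hospitalization, emergency attendance and absence from work. Severe applies when something "threatens the life of the research participant, causes congenital anomalies, results in permanent or significant disability, or requires intervention to prevent sequelae". Death is graded Lethal.

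**Causality.** Table 3 has two categories. Suspected requires timing that makes a causal link possible and no sufficient other explanation. Unsuspected requires timing that makes a link unlikely and a sufficient other explanation.

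**Use.** The synopsis promises that adverse events will be analysed and reported by severity and causality. Form RQ-017 (Annex 4, non-serious events) has an intensity item that includes Severe. Form RQ-018 (Annex 5, serious events) has none.

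**The concern.** Adjacent sections give the same word two meanings. If an investigator applies 10.1.3 as written, the grade that should mark the most intense non-fatal events marks mostly the serious ones. A very intense event and a merely disruptive one then share the grade Moderate, and the severity table cannot tell them apart.

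The example in 10.1.1 is relevant to this drug. Section 1.3.5, taken from the comparator leaflet, lists three reactions as very common: "Very common: palpitations", "Very common: insomnia" and "Very common: headache". Each can be intense without threatening life, causing a congenital anomaly or leaving lasting disability.

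On causality, the two Table 3 definitions are not complements of each other. This has one practical consequence: section 10.4 makes notification of SAEs after the final visit depend on whether the investigator suspects a causal link.

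**Working it through.** The plan gives no figure to reproduce, so the check sets the definitions side by side.

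**Step 1. The four limbs of Severe (10.1.3) against the SAE list (10.1.2).**

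| Limb of Severe | Counterpart in 10.1.2 | Match |
|---|---|---|
| Threat to life | Life-threatening | Direct |
| Congenital anomaly | Congenital abnormality or birth defect | Direct |
| Permanent or significant disability | Persistent or significant disability | Direct |
| Intervention to prevent sequelae | Intervention to prevent another SAE outcome | Partial; 10.1.3 is broader |

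Limbs = 4; direct matches = 3; limbs open to a non-serious event = 4 − 3 = 1. Limbs that measure intensity = 0.

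**Step 2. The other grades.** Hospitalization is an SAE criterion in 10.1.2 and falls under Moderate in 10.1.3. Death is an SAE criterion and forms the grade Lethal. The overlap with seriousness is therefore not confined to Severe.

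**Step 3. The example in 10.1.1.** Take a severe headache that stops normal activity for a day, resolves fully and needs no intervention to prevent sequelae. It meets none of the four limbs of Severe. It does alter normal activity, so the highest grade available is Moderate.

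**Step 4. Table 3, reading *and* literally in both definitions.**

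| Timing | Other explanation | Category as written | If *and* in Unsuspected is read as *or* |
|---|---|---|---|
| Link possible | Not sufficient | Suspected | Suspected |
| Link possible | Sufficient | Neither | Unsuspected |
| Link unlikely | Not sufficient | Neither | Unsuspected |
| Link unlikely | Sufficient | Unsuspected | Unsuspected |

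Undefined combinations: 4 − 2 = 2 on the literal reading and 0 on the other. The gap comes entirely from that one conjunction.

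**The case against.** **The scale is not empty of intensity.** Mild and Moderate already grade by effect on daily life and will separate many non-serious events. This stands. The defect is the top non-fatal grade, not the whole scale.

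**The two concepts are not fully merged.** A reader might infer that no non-serious event can ever be Severe. The documents do not support that: the fourth limb is broader than its SAE counterpart, and RQ-017 offers a Severe box. Equally, a hospitalized participant's event is serious but can be Moderate. It is also fair to say that the headache sentence in 10.1.1 explains usage and is not a grading rule. Even so, 10.1.1 sets out what severity means, and 10.1.3 then defines Severe without it.

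**Causality is largely covered by the labels.** A reader might take two of four combinations to mean that half of events would go unclassified. That does not follow. The count is of combinations, not events. Section 10.1.1 names the categories suspected and non-suspected, and the forms offer Suspect against Not suspect (RQ-017) or Non-Suspect (RQ-018). These are complements and imply a default. Section 10.1.4 also leaves the judgement to the investigator after review of all accessible data. What remains is a wording clarification.

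**Safety analysis.** A reader might infer from the words Not applicable in 13.6 that adverse events will not be reported. The section can be read as no statistical safety analysis, since adverse events are to be entered in the Clinical Report. It adds nothing to this point.

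**Frequency.** Section 1.3.5 says that the reactions are generally associated with excessive dosage, and its frequencies are not for a single dose in healthy participants. They show that the example is relevant, not how often misgrading would occur.

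**Conclusion.** The contradiction between 10.1.1 and 10.1.3 is real and should be corrected. Its size can be stated only in terms of wording: three of four limbs of Severe are SAE criteria, and one is open to non-serious events. This assumes that investigators apply 10.1.3 as written; those who grade by the ordinary sense of severe would produce a different table from the same events.

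The causality point is minor. It rests on the literal reading of Table 3, and matters mainly because notification of SAEs after the final visit turns on suspicion of a causal link.

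A reader might go further and infer that serious events could be missed. The documents do not support this: SAEs are identified under 10.1.2, and those occurring during the study are notified within 24 hours under 10.4 whatever their intensity or causality. The bioequivalence analysis uses neither scale.

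**What to change.** 1. Reconcile 10.1.1 to 10.1.3: define mild, moderate and severe by intensity and interference with usual activity, and keep the seriousness criteria, including hospitalization, in 10.1.2 only.
2. As a consequence, add an intensity item to RQ-018. At present, item 18 of that form records the outcomes that determine most of the grades; once grading is by intensity, it would no longer do so.
3. State in Table 3 that an event not meeting Suspected is classed as non-suspected, which is what the labels imply. If the sponsor prefers another assignment for the two mixed combinations, state that rule instead.

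The cost is rewording of two definitions and one extra form item. Design, sample size and the bioequivalence analysis do not change.
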